6.15.4. Clinical Laboratory Evaluation

Laboratory evaluations will be summarized and analyzed for the following periods:

- Open-Label Treatment Period (Safety Population)
- Post-Treatment Follow-Up Period (Post-Treatment Follow-Up Population)

Laboratory analyses will include planned analytes only. Planned analytes are those specified in the protocol. However, unplanned/unscheduled measurements of planned analytes will be included/ excluded as specified in the relevant sections. Examples of unplanned/unscheduled measurements include those that the clinical investigator orders as a repeat test or “retest” of a laboratory test if he or she has received an abnormal value, and those the investigator orders for a “follow-up visit” due to clinical concerns.

Laboratory test observed values at each visit (starting at baseline) and change from baseline to each visit will be displayed in box plots (with outliers displayed) for patients who have both a baseline and at least 1 post-baseline result for Period 2 and Period 3, respectively. Baseline will be the last nonmissing observation in the baseline period. Original-scale data will be used for the display. Unscheduled visits and repeat measurements will be excluded. In each of the plots displaying values at each visit, lines indicating the performing lab reference ranges will be added. Displays using both standard (SI) and conventional (CN) units will be provided (when different). The following summary statistics will be included in a table below the box plot: N, mean, standard deviation, minimum, Q1, median, Q3, and maximum. P-values and confidence limits will not be included in the summary statistics at the bottom of the box plot. Box plots will be used to evaluate trends over time and to assess a potential impact of outliers on central tendency summaries.

The number and percentages of patients with treatment-emergent abnormal, high, or low laboratory results at any time will be summarized by treatment for the treatment period. Scheduled visits, unscheduled visits, and repeat measurements will be included. Performing lab reference ranges will be used to define the low and high limits.

- Categorical laboratory tests:
 - A treatment-emergent **abnormal** result is defined as a change from normal at all baseline visits to abnormal at any time during the treatment period.
- Numerical laboratory tests:
 - A treatment-emergent **high** result is defined as a change from a value less than or equal to the high limit at all baseline visits to a value greater than the high limit at any time during the treatment period.
 - A treatment-emergent **low** result is defined as a change from a value greater than or equal to the low limit at all baseline visits to a value less than the low limit at any time during the treatment period.

Alanine aminotransferase (ALT), aspartate aminotransferase (AST), total bilirubin, alkaline phosphatase (ALP), neutrophils, leukocytes, platelets, and lymphocytes will not be included in this treatment-emergent abnormal, high, or low laboratory results analysis. A separate analysis

to address the risk of liver injury is described in [Table RHCF.6.7](#) in which performing lab reference ranges will be used.

By-patient listing of abnormal laboratory test results (criteria defined in the shift tables excluding the normal category) for parameters of special interest (hepatic, leukocytes, and platelets) will be provided.

6.15.4.1. Leukocytes (White Blood Cells) and Platelets

Further analyses will be conducted for total leukocytes, neutrophils, platelets, lymphocytes, monocytes, eosinophils, and basophils. Neutrophils will include both segmented neutrophils and absolute neutrophils (derived by adding segmented neutrophils and band neutrophil). The segmented neutrophils and absolute neutrophils will be summarized using the same categories.

Shift tables will be produced showing the number and percentage of patients with a minimum post-baseline result for neutrophils, lymphocytes (including Th17 lymphocytes), platelets, and leukocytes, and will be summarized overall and by treatment group and baseline result. Unless otherwise specified, neutrophils will be summarized for absolute neutrophils. Scheduled visits, unscheduled visits, and repeat measurements will be included. Baseline is defined as the minimum result during the defined baseline period.

The following LLNs will be defined for the analyses:

- Leukocytes: $LLN=4.0 \times 10^9/L$
- Neutrophils: $LLN=2.0 \times 10^9/L$
- Lymphocytes: $LLN=1.1 \times 10^9/L$
- Platelets: $LLN=150 \times 10^9/L$

Such shift tables will be produced using the following categories:

- Neutrophils: $\geq 1 \times LLN$ (Normal), $< LLN$ to $\geq 1.5 \times 10^9/L$ (Grade 1), $< 1.5 \times 10^9/L$ to $\geq 1.0 \times 10^9/L$ (Grade 2), $< 1.0 \times 10^9/L$ to $\geq 0.5 \times 10^9/L$ (Grade 3), and $< 0.5 \times 10^9/L$ (Grade 4).
- Leukocytes: $\geq 1 \times LLN$ (Normal), $< LLN$ to $\geq 3.0 \times 10^9/L$ (Grade 1), $< 3.0 \times 10^9/L$ to $\geq 2.0 \times 10^9/L$ (Grade 2), $< 2.0 \times 10^9/L$ to $\geq 1.0 \times 10^9/L$ (Grade 3), and $< 1.0 \times 10^9/L$ (Grade 4).
- Platelets: $\geq 1 \times LLN$ (Normal), $< LLN$ to $\geq 75.0 \times 10^9/L$ (Grade 1), $< 75.0 \times 10^9/L$ to $\geq 50.0 \times 10^9/L$ (Grade 2), $< 50.0 \times 10^9/L$ to $\geq 25.0 \times 10^9/L$ (Grade 3), and $< 25.0 \times 10^9/L$ (Grade 4).
- Lymphocytes: $\geq 1 \times LLN$ (Normal), $< LLN$ to $\geq 0.8 \times 10^9/L$ (Grade 1), $< 0.8 \times 10^9/L$ to $\geq 0.5 \times 10^9/L$ (Grade 2), $< 0.5 \times 10^9/L$ to $\geq 0.2 \times 10^9/L$ (Grade 3), and $< 0.2 \times 10^9/L$ (Grade 4).

In addition, for the above parameters (neutrophils, leukocytes, platelets, and lymphocytes), the number and percentage of patients with minimum post-baseline results will be presented overall and by treatment within the following group using the categories as defined above:

- Decreased: post-baseline category $<$ baseline category
- Increased: post-baseline category $>$ baseline category
- Same: post-baseline category = baseline category

The number and percentages of patients with treatment-emergent low laboratory results at any time will be summarized for these 4 measures by treatment group for the Open-Label Treatment Period (Period 2) and Post-Treatment Follow-Up Period (Period 3). Shift tables will be produced showing the number and percentage of patients with a minimum post-baseline result for these 4 measures and will be summarized overall and by treatment group and baseline result.

The change from minimum baseline to minimum post-baseline result for each of these leukocytes and platelets will be summarized graphically using a box plot for Safety Population in Period 2.

6.15.4.2. Neutrophil Follow-Up

Neutrophil counts will be followed throughout the study. Patients will continue to be followed in Period 3 until their neutrophil counts have recovered.

The neutrophil follow-up analysis will be conducted on the Neutrophil Follow-Up Population defined as patients who have an absolute neutrophil count <1500 cells/ μL (SI units: $<1.5 \times 10^9/\text{L}$) at the last scheduled visit or early termination visit prior to entering the Post-Treatment Follow-Up Period (Period 3) and less than the patient's baseline absolute neutrophil count (that is, prior to first injection at Week 0). These patients are monitored during the Period 3 until neutrophil recovery.

Neutrophil clinical recovery is defined as an absolute neutrophil count ≥ 1500 cells/ μL (SI units: $\geq 1.5 \times 10^9/\text{L}$) or greater than or equal to a patient's minimum absolute neutrophil count prior to first study drug injection at Week 0.

If a patient's neutrophil count has not recovered, within 12 weeks after entering the follow-up period (Visit 802), the patient will return for Visit 803 (12 weeks after Visit 802). Additional visits may be required for appropriate patient management depending upon the degree of neutropenia. If at Visit 802, a patient has met the criteria for neutrophil recovery, the patient's participation in the study will be considered complete, unless the investigator deems additional follow-up may be necessary.

The number and percentage of patients achieving neutrophil clinical recovery will be presented by dosing regimen and week interval for Neutrophil Follow-Up Population in the Post-Treatment Follow-Up Period (Period 3). The number and percentage of patients with an absolute neutrophil cell count that is at least 25%, 50%, 75%, or 100% of the patient's baseline absolute neutrophil count (that is, prior to first injection at Week 0), irrespective of absolute neutrophil minimum, will be included in the summary.

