5.1.3. Post-Treatment Follow-Up Period (Period 3)

All patients receiving at least 1 dose of investigational product will enter the Post-Treatment Follow-Up Period (Period 3), occurring from last treatment visit (LTV) during Period 2 or ETV up to a minimum of 12 weeks after that visit.

The required study visits should occur 4 weeks (Visit 801) and 12 weeks (Visit 802) after the last regularly scheduled visit in Period 2 (or the date of the patient's ETV), except for patients with a concurrent infection that requires systemic anti-infective therapy (described below).

If, at Visit 802, a patient's neutrophil count is ≥ 1500 cells/ μ L or greater than or equal to the patient's baseline neutrophil count, the patient's participation in the study will be considered complete unless the investigator determines additional follow-up may be necessary. An additional study visit (Visit 803) 12 weeks after Visit 802 may be required.

If, at the last scheduled visit or ETV, a patient's neutrophil count is <1500 cells/ μ L ($<1.50 \times 10^3/\mu$ L or <1.50 GI/L) and less than the patient's baseline neutrophil count, the following measures should be taken:

- Patients with concurrent infection: If there is a concurrent infection that requires systemic anti-infective therapy, the patient should receive appropriate medical care and a repeat test for neutrophil count should be performed at least Q4W (or sooner as appropriate) until resolution of infection. Upon resolution of infection, the neutrophil count should be monitored using the required study visits in the Post-Treatment Follow-Up Period (Period 3) design at Visits 801 (4 weeks after resolution of infection), 802 (8 weeks after Visit 801), and 803 (if necessary; 12 weeks after Visit 802); additional visits may be required depending on the degree of neutropenia.
- Patients without concurrent infection: If there is no concurrent infection that requires systemic anti-infective therapy, the neutrophil count should be monitored using the required study visits in the Post-Treatment Follow-Up Period (Period 3) design, Visits 801 (4 weeks post ETV or last regularly scheduled visit), 802, and 803 (if necessary); additional visits may be required depending on the degree of neutropenia.
- For Visit 801 and subsequent visits, the following monitoring applies:
 - As long as a patient's neutrophil count is <1000 cells/μL (<1.00 × 10³/μL or

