 <1.00 GI/L) at any follow-up visit, the patient should return for additional visits at least Q4W (unscheduled visits may be required).
 - O As long as a patient's neutrophil count is ≥ 1000 cells/μL and <1500 cells/μL ($\geq 1.00 \times 10^3$ /μL and $<1.50 \times 10^3$ /μL or ≥ 1.00 GI/L and <1.50 GI/L) at any follow-up visit, the patient should return for additional visit(s) at least every 4 to 8 weeks (unscheduled visits may be required).

- o If at Visit 803 the patient's neutrophil count remains <1500 cells/ μ L (<1.50 × 10³/ μ L or <1.50 GI/L) and less than the patient's baseline neutrophil count or if the investigator deems additional follow-up may be necessary, the investigator in consultation with Eli Lilly and Company (Lilly) or qualified designee will determine the appropriate management of the patient and the appropriate timing of additional contact(s) or visit(s).
- If at Visit 802 or Visit 803 the patient's neutrophil count is ≥1500 cells/µL (≥1.50 × 10³/µL or ≥1.50 GI/L) or greater than or equal to the patient's baseline neutrophil count (whichever is lower), the patient's participation in the study will be considered complete unless the investigator deems additional follow-up necessary.

For patients who completed or discontinued study treatment and have entered the Post-Treatment Follow-Up Period (Period 3), PsA therapy with another agent is allowed, as determined appropriate by the investigator.

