- [39] Are positive for human immunodeficiency virus serology (HIV), ie, positive for human immunodeficiency virus antibody (HIVAb).
- [40] Have evidence of or test positive for hepatitis B virus (HBV) by testing positive for: 1) HBV surface antigen (HBsAg+); OR 2) anti-hepatitis B core antibody (HBcAb+) and are HBV deoxyribonucleic acid (DNA) positive.

Note: Patients who are HBsAg-, and HBcAb+ and HBV DNA negative may be enrolled in the study. Patients who meet these criteria at screening will be identified by the central laboratory and monitored during the study as detailed in Section 9.4.5.4.

- [41] Have evidence of or test positive for hepatitis C virus (HCV). A positive test for HCV is defined as: positive for hepatitis C antibody (anti-HCVAb) and positive via a confirmatory test for HCV (for example, HCV polymerase chain reaction).
- [42] Laboratory tests may not be repeated unless there is a technical error or clinical reason to believe a result may be erroneous. Laboratory tests can be repeated a maximum of 1 time, and results must be received and reviewed prior to randomization (Visit 2). For eligibility, the most recent lab panel must not meet any of the following criteria:
 - [42a] Neutrophil count <1500 cells/μL
 - [42b] Lymphocyte count <800 cells/μL
 - [42c] Platelet count <100,000 cells/μL
 - [42d] Aspartate aminotransferase (AST) or alanine aminotransferase (ALT) >2.5 times the upper limit of normal (ULN)

- [42e] Total white blood cell count <3000 cells/µL
- [42f] Hemoglobin <8.5 g/dL (85.0 g/L) for male patients and <8.0 g/dL (80 g/L) for female patients
- [42g] Serum creatinine >2.0 mg/dL
- [42h] Have clinical laboratory test results at screening that are outside the normal reference range for the population and are considered clinically significant, per investigator assessment.
- [43] Have any condition or contraindication as addressed in the local labelling for adalimumab that would preclude the patient from participating in this protocol.
- [44] Have any other condition that precludes the patient from following and completing the protocol, in the opinion of the investigator.
- [45] Are women who are breastfeeding.
- [46] Are study site personnel directly affiliated with this study and/or their immediate families. Immediate family is defined as a spouse, parent, child, or sibling, whether biological or legally adopted.
- [47] Are Lilly employees or its designee or are employees of third-party organizations involved in the study.

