10.3.1.1. General Considerations for Analyses during Period 2 (Open-Label Treatment Period)

Baseline will be defined as the last available value before the first injection of the study drug for both efficacy, health outcomes, and safety analyses. In most cases, this will be the measurement recorded at Week 0 (Visit 2).

Categorical data for baseline variables will be summarized as frequency counts and percentages. Continuous data for baseline variables will be summarized using the mean, standard deviation, minimum, maximum, median, and number of observations.

Comparisons of ixekizumab versus adalimumab will be performed for all outcome variables at all visits in Period 2; however, the primary time point of interest is Week 24.

Change from baseline at a particular visit will be calculated as the value at that visit minus the baseline value.

For outcome measures that are not collected at each post-baseline visit, data may exist at visits where the outcome measure was not scheduled to be collected, due to early discontinuation visits. In these situations, data from the early discontinuation visit that does not correspond to the planned collection schedule will be excluded from any mixed-effects models for repeated measures (MMRM) analysis. However, the data will still be used in other analyses, including shift analyses, change from baseline analyses using last observation carried forward (LOCF) imputation method, and other categorical analyses.

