6.1.1. General Considerations for the Open-Label Treatment Period (Period 2)

Baseline will be defined as the last available value on or prior to the first injection of the study drug for both efficacy, health outcomes, and safety analyses. In most cases, this will be the measurement recorded at Week 0 (Visit 2).

Categorical and continuous data will be summarized as described in Section 6.1.

Comparisons of ixekizumab versus adalimumab will be performed for all outcome variables in Period 2, as deemed appropriate, using methods described in Section 6.2.

Safety will be assessed by summarizing and analyzing adverse events (AEs), laboratory analytes including neutrophil counts, vital signs, and concomitant medications. The duration of exposure will also be summarized.

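### SAP 6.15.4.2 tests entry to the neutrophil follow-up analysis against baseline but recovery against the lowest pre-dose count, so in an uncommon case a patient can enter already recovered, in conflict with Protocol 5.1.3

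*SAP*

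**What the plan says.** Three rules bear on this point.

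- **SAP entry rule (6.15.4.2).** The last Period 2 count must be below 1500 cells/µL and "less than the patient's baseline absolute neutrophil count (that is, prior to first injection at Week 0". On baseline, SAP 6.1.1 says: "Baseline will be defined as the last available value on or prior to the first injection of the study drug". Protocol 10.3.1.1 agrees in substance: "Baseline will be defined as the last available value before the first injection of the study drug".
- **SAP recovery rule (6.15.4.2).** Recovery is a count of at least 1500, or at least the patient's "minimum absolute neutrophil count prior to first study drug injection at Week 0". The same section says patients are followed in Period 3 until recovery, and that meeting the recovery criteria at Visit 802 completes participation unless the investigator wants more follow-up.
- **Protocol rule (5.1.3).** Monitoring starts when the count is below 1500 and below baseline. At Visit 802 the criterion is a count of at least 1500 "or greater than or equal to the patient's baseline neutrophil count, the patient's participation in the study will be considered complete". For Visits 802 and 803 this is restated as "greater than or equal to the patient's baseline neutrophil count (whichever is lower"). The last words compare 1500 with baseline; they do not bring in a minimum over several pre-dose values.

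Exclusion [42] in Protocol 6.2 judges eligibility on the most recent panel, where a neutrophil count below 1500 excludes. It adds: "Laboratory tests can be repeated a maximum of 1 time". A repeat is permitted only for a technical error or a clinical reason to doubt the result.

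**The concern.** Baseline and minimum are different quantities whenever a patient has more than one pre-dose count. The Schedule of Activities makes that routine, with hematology at both Visit 1 and Visit 2. If the bar for recovery lies below the bar for entry, some counts satisfy both at once, and a patient can be counted as recovered on the value that placed them in the population.

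Two things are at stake. The first is the percentage achieving neutrophil recovery: neutropenia is among the adverse events of special interest (Protocol 9.2.1.1), and the Neutrophil Follow-Up Population is a subset in which one or two patients could move a percentage. The second is consistency. The Schedule of Activities ties Visit 803 to the criteria in Protocol 5.1.3, while SAP 6.15.4.2 describes completion at Visit 802 by its own recovery definition. The same patient can be finished under one document and not under the other.

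**Working it through.** The plan states no figure to reproduce, so the check is on the logic of the rules.

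**Notation.** Let *x* be the count being judged, *b* the last pre-dose count (baseline) and *m* the lowest pre-dose count, so *m* ≤ *b*. In cells/µL:

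- SAP entry: *x* < 1500 and *x* < *b*, that is, *x* < min(1500, *b*).
- SAP recovery: *x* ≥ 1500 or *x* ≥ *m*, that is, *x* ≥ min(1500, *m*).
- Protocol completion: *x* ≥ 1500 or *x* ≥ *b*, that is, *x* ≥ min(1500, *b*).

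Protocol completion is the exact complement of SAP entry, so nobody can satisfy both on one value. SAP entry and SAP recovery overlap when *m* ≤ *x* < min(1500, *b*). That band exists only if *m* < 1500 and *m* < *b*: a pre-dose count below 1500 that is lower than the last one. Otherwise the rules agree. Because *m* never exceeds *b*, the SAP can count as many recoveries as the protocol rule or more, never fewer.

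**Example (assumed values).** First screening 1300, permitted repeat 1600, Week 0 1700, last-visit count 1400.

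| Rule | Test | Result |
|---|---|---|
| SAP entry | 1400 < 1500 and 1400 < 1700 | enters |
| SAP recovery | 1400 ≥ min(1300, 1600, 1700) = 1300 | recovered |
| Protocol completion | 1400 ≥ 1500 or 1400 ≥ 1700 | not met |

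The overlap band for this patient runs from 1300 up to, but not including, min(1500, 1700) = 1500. The last-visit count is 1400/1700 = 82.4% of baseline.

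**Enumeration.** Pre-dose counts from 1000 to 2100 and last-visit counts from 500 to 2100 were enumerated in steps of 100.

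- One screening value of at least 1500, any Week 0 value: 0 of 735 entrant combinations are recovered at entry under the SAP.
- First screening value below 1500, repeat of at least 1500, any Week 0 value: 875 of 3675 are.
- Protocol rule: 0 in both sets.
- One reference value in both SAP rules, whether baseline or minimum: 0.

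These are counts of grid combinations and say nothing about how often such patients occur.

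**The case against.** The strongest defence is that the minimum is a deliberate convention. SAP 6.15.4.1 takes the minimum of the baseline period as baseline for its leukocyte and platelet shift tables and plots change from that minimum. If that meaning carried into 6.15.4.2, entry and recovery would agree. The text does not bear this out: the definition sits with the shift tables, and 6.15.4.2 uses baseline and minimum as separate terms, reporting percent of baseline regardless of the minimum. Even on that reading, the SAP would still differ from Protocol 5.1.3.

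Three limits do stand:

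- Exclusion [42] gives no general right to retest a low count. The main route therefore needs a first result thought to be erroneous. Other routes are an unusual sequence of pre-dose values or an inadvertently enrolled patient.
- SAP 6.15.4.2 also reports patients reaching at least 25%, 50%, 75% or 100% of baseline. The example patient, at 82.4%, would show as reaching 75% but not 100%, so a baseline-referenced result stands beside the recovery figure. This discloses the issue in part, though it is not the protocol's combined criterion.
- Nothing inferential depends on it. Table RHCF.6.1 gives no treatment comparison for Period 3, and SAP 6.15 treats safety analyses as descriptive.

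A reader might infer that the reported recovery percentage is overstated as a matter of fact, or that sites would release neutropenic patients early. The documents support neither. They give no number of affected patients, which could be zero, and Protocol 5.1.3 sets out the follow-up rule and leaves room for further visits at the investigator's judgement.

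**Conclusion.** The point holds as a narrow inconsistency. SAP 6.15.4.2 uses one reference value for entry and another for recovery, and the recovery reference differs from the one in Protocol 5.1.3. Where a pre-dose count is below 1500 and is not the last pre-dose value, a patient can enter the analysis already recovered. The descriptive recovery percentage could then be too high, never too low, relative to the protocol criterion, and the documents can disagree on completion at Visit 802.

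This rests on reading baseline in 6.15.4.2 as the last pre-dose value, as SAP 6.1.1 defines it. The number of patients concerned is unknown and probably very small. The matter is minor: no efficacy result and no treatment comparison changes.

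**What to change.** Reconcile SAP 6.15.4.2 with Protocol 5.1.3, so that the analysis uses a single reference count for both entry and recovery and the two documents state the same completion criterion. Name that count explicitly in 6.15.4.2, since 6.15.4.1 uses baseline in another sense. Which count governs patient follow-up is a clinical matter for the sponsor and is not proposed here; either choice removes the overlap inside the SAP.

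The cost is small. No new data are needed. If the reference already used for entry and in the protocol is kept, one phrase in the SAP changes; otherwise the SAP entry rule and Protocol 5.1.3 must change as well. The reported recovery percentage may shift slightly or not at all.
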